6.1.1.3 Subgroup analyses

[figure not shown]
No subgroup analysis is planned for primary effectiveness endpoint.

6.1.2 Secondary Effectiveness Endpoints

Secondary effectiveness endpoints will be analyzed based on observed cases in the PPS and on observed cases in the FAS.

For both GAIS scores (iGAIS and sGAIS), the proportion of subjects with any improvement at Week 24 will be calculated by treatment and given as number of subjects with any

improvement/number of subjects in the corresponding analysis (n/N_{obs}^3) and as percentage (%). The 2-sided 95% exact Pearson Clopper CI for the response rate will be reported as well. In addition, the crude difference of the two treatment response proportions will be stated along with the associated two-sided 95% Newcombe-Wilson CIs for paired data [Method No. 10 in Newcombe (1998; [2])]. Cross tables will be provided showing number (and percentage) of subjects with any (or no) GAIS improvement of the Radiesse side versus any (or no) GAIS improvement of the Restylane side. For definition of “any improvement” on iGAIS and sGAIS see [Section 5.1.2](#).

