#### 13.4.1.2 *Secondary Effectiveness Endpoints*

For both GAIS scores, the proportion of subjects with any improvement at Week 24 will be calculated by treatment and given as number of subjects with improvement/number of subjects in the corresponding analysis (n/N) and as percentage (%). In addition, the difference of the two treatment response proportions will be stated. Cross tables will be provided showing number (and percentage) of subjects with any (or no) GAIS improvement of the Radiesse-treated side versus any (or no) GAIS improvement of the Restylane-treated side.

[REDACTED]

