3.2 Effectiveness

The sample size considerations for the primary effectiveness endpoint (i.e., change from baseline to Week 24 after last injection on the WSRS [REDACTED]) are based on the following:

- Type I error, $\alpha = 0.05$ (two-sided) and
- Non-inferiority margin of 0.5.

When using the 118 subjects randomized for safety and applying a drop-out rate of 15% from randomization to the Per Protocol Set (PPS), [REDACTED]

[REDACTED] 100 subjects would be available for analysis of the primary effectiveness endpoint on PPS.

For analysis on the Full Analysis Set (FAS) even more subjects are expected. [REDACTED]

To ensure a reasonable number of subjects is enrolled per investigative site, the number of subjects treated at each site should not exceed 20 in case of seven recruiting sites, 24 in case of six recruiting sites, and 28 in case of five recruiting sites.

4 Analysis Sets

The following analysis sets will be defined:

- The randomized set is defined as all subjects randomized into the trial.
- The Safety Evaluation Set (SES) is defined as all subjects who are randomized and receive investigational product at least once.
- The Full Analysis Set (FAS) is defined as all subjects who are randomized, receive investigational product, and have at least one after-baseline effectiveness assessment.
- The Per Protocol Set (PPS) is the subset of subjects in the FAS who have no major protocol deviations or other events that impact analysis of the primary effectiveness endpoint. Final determination of which events lead to exclusion from PPS will be made prior to database close.

Analyses on the randomized subjects set, the FAS and the PPS will be performed *by randomized treatment*. For subjects randomized to “Group 1: left NLF: Radiesse, right NLF: Restylane”, the left NLF will be analyzed for Radiesse and the right NLF will be analyzed for Restylane, and for subjects randomized to “Group 2: left NLF: Restylane, right NLF: Radiesse”, the left NLF will be analyzed for Restylane and the right NLF will be analyzed for Radiesse.

5 Endpoints for Analysis

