5.2.2 Secondary Safety Endpoint

- Incidence of TEAEs related to Radiesse, as reported by the treating investigator throughout the trial.

6 Statistical Analysis Methods

Metric statistics for continuous endpoints will be number of values analyzed (n), number of observed values (Nobs), mean, standard deviation (SD), median, lower quartile (Q1), upper quartile (Q3), minimum (min), and maximum (max), if not stated otherwise. Mean, quartiles and median will be reported to one decimal place more than the data were collected, for the standard deviation two decimal places more will be displayed; for derived data, the number of decimal places will explicitly be given in the sections below.

¹ Injection depth is included in list of additional data collected ([Section 11.2.3](#) of CSP version 2.0) but is not analyzed because these data are not collected in the case report form.

Frequency tables for qualitative endpoints will be absolute and percent frequencies (n, %). Cross tables will include number of subjects with non-missing data at the corresponding visit. Percentages will be calculated using the denominator of all subjects in a specified population or random group (only needed for selected disposition tables in [14.1](#)). For TEAE analyses on the SES, which will be conducted by actual treatment (see [Section 4](#)), the denominator for calculation of percentages per treatment will be adapted to the number of subjects in SES treated with the respective treatment. For analyses on observed cases (OC), percentages will be calculated using the number of subjects with non-missing data (Nobs) at the corresponding visit as denominator. The denominator will be specified in a footnote to the tables for clarification if not otherwise obvious.

The total number of subjects in a given analysis set (as defined in [Section 4](#)) will be referred to with N.

Percentages will be reported to one decimal place. If not otherwise specified, statistical tests will be conducted two-sided at type I error rate 5%. P values will be reported to four decimal places (e.g., p=0.0375). P values below 0.0001 will be presented as '<0.0001'. P values above 0.9999 will be presented as '>0.9999'. Confidence intervals (CIs) will be two-sided 95% CIs.

Detailed information on effectiveness, safety, and other data will be provided in listings.

All statistical analyses will be performed using Statistical Analysis System (SAS) statistical analysis software (Version 9.4).

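### GAIS improvement rates in the FAS leave out subjects with no Week 24 rating, so the FAS run does not test sensitivity to missing ratings

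*SAP*

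**What the plan says.** SAP 6.1.2 sets the basis for both GAIS endpoints: "Secondary effectiveness endpoints will be analyzed based on observed cases in the PPS and on observed cases in the FAS". The rate is written "improvement/number of subjects in the corresponding analysis (n/N_{obs}^3) and as percentage"; the raised 3 is a footnote marker.

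The introduction to SAP Section 6 defines both symbols. For observed-case analyses, "percentages will be calculated using the number of subjects with non-missing data (Nobs) at the corresponding visit as denominator". Separately, "The total number of subjects in a given analysis set (as defined in [Section 4](#)) will be referred to with N".

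SAP Section 4 admits to the FAS randomized, treated subjects who "have at least one after-baseline effectiveness assessment". A Week 24 rating is not required. SAP 6.1 refers to effectiveness data collected at Week 4, so a subject seen then and lost before Week 24 can be in the FAS.

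Protocol 13.4 gives the FAS the role of sensitivity analysis to the PPS. Protocol 13.4.1.2 writes the GAIS rate as "number of subjects with improvement/number of subjects in the corresponding analysis (n/N) and as percentage". SAP 6.1.2 adds an exact Clopper-Pearson interval for each rate and a Newcombe interval for the paired difference. SAP 6.4.4 treats everything beyond the one confirmatory analysis as exploratory or sensitivity work.

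**The concern.** A sensitivity population is useful when it restores what the main population removed. For GAIS, the FAS restores subjects excluded from the PPS for major deviations, provided they have a Week 24 rating. It does not bring in subjects without that rating, because the observed-case rule removes them again.

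Two groups can leave the PPS rate, deviators and the unrated, and the planned FAS run examines only the first. If subjects without a rating did worse than those rated, each product's improvement rate would be too high in both runs, and their agreement would give no warning. Protocol 8.2 calls subject satisfaction the main goal of aesthetic medicine, and Protocol 9.2.6.1 names refusal of a touch-up as a possible reason for stopping treatment. A link between poor result and departure is therefore plausible. The documents do not show one.

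What is at stake is the single-product improvement rate, the figure most easily carried into a summary of the device.

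**Working it through.** **Inputs from the documents.** 118 randomized; 15% loss from randomization to the PPS; 100 in the PPS (Protocol 13.1.2, SAP 3.2). The FAS is expected to exceed 100, with no figure given. No GAIS rate, GAIS power or number without a Week 24 rating is visible.

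**The plan's own figure.** 118 × 0.85 = 100.3, and 100/0.85 = 117.6, rounded up to 118. It reproduces.

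**Assumptions.** FAS N = 118. Missing Week 24 ratings m = 0 to 18, where 18 = 118 − 100. Observed improvement about 90%, then 70% and 95% as a range.

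**Formulas.** Nobs = N − m. With x improved among those rated:
- planned rate = x/Nobs, with interval from the Beta(x, Nobs − x + 1) 2.5% quantile to the Beta(x + 1, Nobs − x) 97.5% quantile;
- none of the missing improved = x/N, which is the planned rate × Nobs/N;
- all of the missing improved = (x + m)/N.

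| Missing | Planned x/Nobs (95% CI) | None of the missing improved, x/118 (95% CI) | All of the missing improved |
|---|---|---|---|
| 0 | 106/118 = 89.8% (82.9 to 94.6) | 89.8%, unchanged | 89.8% |
| 6 | 101/112 = 90.2% (83.1 to 95.0) | 85.6% (77.9 to 91.4) | 90.7% |
| 12 | 95/106 = 89.6% (82.2 to 94.7) | 80.5% (72.2 to 87.2) | 90.7% |
| 18 | 90/100 = 90.0% (82.4 to 95.1) | 76.3% (67.6 to 83.6) | 91.5% |

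At about 90% observed, x/N first falls below the planned interval at 10 missing: 97/118 = 82.2% against a lower limit of 82.5% for 97/108.

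**Other observed rates, 18 missing.** 70/100 = 70.0% becomes 70/118 = 59.3%, or 74.6% if all improved. 95/100 = 95.0% becomes 95/118 = 80.5%, or 95.8%.

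**Paired difference.** A dropout normally loses both folds. Take 100 rated pairs: 80 improved on both sides, 10 on Radiesse only, 5 on Restylane only, 5 on neither. The difference is (10 − 5)/100 = +5.0 points (Newcombe −3.0 to 13.2). Adding 18 pairs as improved on neither gives 5/118 = +4.2 points (−2.4 to 10.9). The estimate moves little, but it moves towards zero and its interval narrows, so this rule is unsuitable for the difference.

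**The case against.** The case against has four parts.

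**The denominators may not conflict.** A reader might infer from n/N in the protocol and n/Nobs in the SAP that the SAP departed from the protocol. The documents do not establish that. The protocol describes its denominator as the subjects in the corresponding analysis, the SAP keeps that description, and N as set size is a SAP definition. The protocol never says that a missing rating stays in the denominator, and the text of the footnote on Nobs is not visible. This objection stands in full.

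**Other text may deal with missing ratings.** A reader might infer that WSRS is imputed while GAIS has nothing. Protocol 13.4.1.1 lists variables for a VAR statement, but the visible text does not mention imputation, and text after the GAIS paragraph in 13.4.1.2 is redacted. A GAIS sensitivity analysis cannot be ruled out, so the point rests only on the stated observed-case rule.

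**The FAS run still has a use.** It would be wrong to call it a second completers' analysis, because it restores rated subjects with major deviations. The gap concerns missing ratings alone.

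**Little depends on it.** GAIS has no visible hypothesis or margin, and the comparative result barely moves. A reader who has N can divide by it, since the SAP promises footnotes for unclear denominators and listings of the data. That is true of the point estimate. It does not supply an interval, a label or a rule fixed before unblinding.

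The direction of bias is also unproven: Protocol 9.2.6.2 lists neutral reasons for leaving, such as moving away.

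**Conclusion.** The point holds as a limited one. Under the stated rule, FAS subjects without a Week 24 rating leave both parts of the GAIS rate, and the FAS analysis cannot show what their absence does to it.

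With an assumed FAS of 118 and about 90% observed improvement, counting the missing as not improved lowers each product's rate by about 5 points for 6 missing, 9 for 12 and 14 for 18. The opposite extreme raises it by at most 1.5 points (91.5% against 90.0%). Eighteen is an upper bound under the plan's loss allowance, not an expected number: the 15% runs to the PPS and may include protocol deviations, and subjects with no post-baseline assessment are already outside the FAS. With complete Week 24 ratings there is no effect.

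A reader might go further and conclude that the reported rates are biased upwards. The documents support only that they may be. The confirmatory WSRS conclusion is unaffected. This is an inexpensive improvement to exploratory endpoints, not an error that threatens the trial.

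**What to change.** In SAP 6.1.2, keep the observed-case analyses in both sets. For the FAS, add a sensitivity row for iGAIS and one for sGAIS that:
- gives each product's rate as n/N, with N the FAS size and a missing Week 24 rating counted as not improved;
- carries a Clopper-Pearson interval and is labelled a lower bound;
- states the number of subjects without a rating.

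Say explicitly that this rule does not apply to the treatment difference. If a redacted section already contains such an analysis, a cross-reference in 6.1.2 is enough.

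The cost is one extra table row per scale and a less favourable responder rate beside the planned one. No new data are needed. Joint imputation of the two folds is not proposed, because pooling exact and Newcombe intervals over imputations would need its own specification, which is out of proportion for exploratory endpoints.

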6.2 Safety Endpoints

[figure not shown]
Safety endpoints are defined in [Section 5.2](#). Safety analyses will be analyzed for the SES if not stated otherwise.

AEs will be coded according to the Medical Dictionary for Regulatory Activities (MedDRA) version that is in effect at the time the database is closed.

Only TEAEs will be analyzed. Non-TEAEs will be listed only. For definitions of TEAEs and non-TEAEs see [Section 5.2](#).

The investigator will report for each TEAE whether only the right NLF, only the left NLF, or both NLFs were affected or whether the treatment area was not affected.

Incidences of TEAEs will be presented in frequency tables. TEAEs affecting the treatment area (either or both NLF) will be analyzed by actual treatment of the respective NLF. Further, incidences of TEAE not affecting the treatment area (i.e. not affecting any NLF) and incidences of TEAEs in total will be presented. The total column will not only include TEAEs affecting either or both treatment NLFs but also TEAEs not affecting the treatment area.

Listings and, if applicable, tables displaying incidences for TEAEs leading to discontinuation, TESAEs, and deaths will also be provided.

[figure not shown]
Further details on analyses of TEAEs are presented in [Section 6.2.1](#) and [Section 6.2.3](#). [REDACTED]

[figure not shown]
6.2.1 Primary Safety Endpoint

[figure not shown]
Not applicable.

6.2.2 Secondary Safety Endpoints

Incidences of TEAEs related to Radiesse will be calculated at the SOC level and at the PT level and will be presented in frequency tables (for specification of columns see first part of [Section 6.2](#) above). [REDACTED]

Protocol deviations and other reasons for exclusion from analysis sets will be summarized in a frequency table, by random group and in total. All protocol deviations will be listed.

Demographic data and other baseline characteristics will be summarized for the SES, FAS, and PPS. If the “randomized subjects set” is not equal to the SES, demographic data and other baseline characteristics will also be summarized for the “randomized subjects set”. [REDACTED]

[figure not shown]
[REDACTED]
[REDACTED]
[REDACTED] Detailed information will be provided in listings.

Medical history, concomitant diseases and prior and concomitant non-drug treatment will be coded using the MedDRA dictionary and reported in frequency tables by SOC and PT levels for the SES. Frequencies of prior and concomitant medication will be given based on different Anatomic Therapeutic Chemical (ATC) code levels for the SES.

Indications for prior and concomitant therapies will not be coded and will only be listed.

Frequency tables will be used to analyze injection technique. These calculations will be based on the SES. Injection location will not be analyzed but listed by subject and treatment visit. In these listings, it will be displayed as “treatment area and side” (left NLF/ right NLF).

6.4 Special Statistical/Analytical Issues

6.4.2 Baseline

Baseline is defined as the last observed value or test result before the initial injection of IMDs. For efficacy endpoints based on WSRS, this corresponds to the score assessed at Screening visit V1.

6.4.3 Interim Analyses

[figure not shown]
No interim analysis is planned for this study.

6.4.4 Multiple Comparisons/Multiplicity

No multiplicity adjustments are required. Only one confirmatory analysis of the primary effectiveness endpoint will be performed. All other analyses are for exploratory or sensitivity purposes.

6.4.6 Pooling of Sites

No pooling of sites is planned for this study.

8 References

- [2] Newcombe, R.G. (1998). Improved confidence intervals for the difference between binomial proportions based on paired data. *Statistics in Medicine*, 17, 2635-2650.

9 Appendix
